7.6. Toxicity Management

All clinical and clinically significant laboratory toxicities will be managed according to uniform guidelines detailed in [Appendix 4](#).

Any questions regarding toxicity management should be directed to the Gilead Sciences Medical Monitor.

7.7. Special Situations Reports

7.7.1. Definitions of Special Situations

Special situation reports include all reports of medication error, abuse, misuse, overdose, reports of adverse events associated with product complaints, occupational exposure with an AE, pregnancy reports regardless of an associated AE, and AEs in infants following exposure from breastfeeding.

Medication error is any unintentional error in the prescribing, dispensing, or administration of a medicinal product while in the control of the health care provider, subject, or consumer.

Abuse is defined as persistent or sporadic intentional excessive use of a medicinal product by a subject.

Misuse is defined as any intentional and inappropriate use of a medicinal product that is not in accordance with the protocol instructions or the local prescribing information.

An overdose is defined as an accidental or intentional administration of a quantity of a medicinal product given per administration or cumulatively which is above the maximum recommended dose as per protocol or in the product labelling (as it applies to the daily dose of the subject in question). In cases of a discrepancy in drug accountability, overdose will be established only when it is clear that the subject has taken the excess dose(s). Overdose cannot be established when the subject cannot account for the discrepancy except in cases in which the investigator has reason to suspect that the subject has taken the additional dose(s).

Product complaint is defined as complaints arising from potential deviations in the manufacture, packaging, or distribution of the medicinal product.

Occupational exposure is defined as exposure to a medicinal product as a result of one's professional or non-professional occupation.

7.7.2. Instructions for Reporting Special Situations

7.7.2.1. Instructions for Reporting Pregnancies

The investigator should report pregnancies in female study subjects that are identified after initiation of study medication and throughout the study, including the post IMP follow-up period, to the Gilead DSPH using the pregnancy report form within 24 hours of becoming aware of the pregnancy.

Refer to Section 7.3 and the eCRF completion guidelines for full instructions on the mechanism of pregnancy reporting.

The pregnancy itself is not considered an AE nor is an induced elective abortion to terminate a pregnancy without medical reasons.

Any premature termination of pregnancy (eg, a spontaneous abortion, an induced therapeutic abortion due to complications or other medical reasons) must be reported within 24 hours as an SAE. The underlying medical reason for this procedure should be recorded as the AE term.

A spontaneous abortion is always considered to be an SAE and will be reported as described in Section 7.3. Furthermore, any SAE occurring as an adverse pregnancy outcome post study must be reported to Gilead DSPH.

The subject should receive appropriate monitoring and care until the conclusion of the pregnancy. The outcome should be reported to Gilead DSPH using the pregnancy outcome report form. If the end of the pregnancy occurs after the study has been completed, the outcome should be reported directly to Gilead DSPH. Gilead DSPH contact information is provided in Section 7.3.

Pregnancies of female partners of male study subjects exposed to Gilead or other investigational agents must also be reported and relevant information should be submitted Gilead DSPH using the pregnancy and pregnancy outcome forms within 24 hours. Monitoring of the subject should continue until the conclusion of the pregnancy. If the end of the pregnancy occurs after the study has been completed, the outcome should be reported directly to Gilead DSPH.

Refer to Appendix 6 for Pregnancy Precautions, Definition for Female of Childbearing Potential, and Contraceptive Requirements.

7.7.2.2. Reporting Other Special Situations

All other special situation reports must be reported on the special situations report form and forwarded to Gilead DSPH within 24 hours of the investigator becoming aware of the situation. These reports must consist of situations that involve study IMP and/or Gilead concomitant medications, but do not apply to non-Gilead concomitant medications.

Special situations involving non-Gilead concomitant medications does not need to be reported on the special situations report form; however, for special situations that result in AEs due to a non-Gilead concomitant medication, the AE should be reported in the eCRFs.

Any inappropriate use of concomitant medications prohibited by this protocol should not be reported as “misuse,” but may be more appropriately documented as a protocol deviation.

Refer to Section 7.3 and the eCRF completion guidelines for full instructions on the mechanism of special situations reporting.

All clinical sequelae in relation to these special situation reports will be reported as AEs or SAEs at the same time using the AE eCRF and/or the SAE report form. Details of the symptoms and signs, clinical management, and outcome will be reported, when available.

8. STATISTICAL CONSIDERATIONS

8.1. Analysis Objectives and Endpoints

8.1.1. Analysis Objectives

The primary objective of this study is as follows:

- To evaluate the effect of presatovir on nasal RSV viral load in RSV-positive LT recipients with acute respiratory symptoms

The secondary objectives of this study are as follows:

- To evaluate the effect of presatovir on clinical sequelae of RSV infection and on measures of lung function
- To evaluate the PK, safety, and tolerability of presatovir

8.1.2. Primary Endpoint

The co-primary efficacy endpoints are

- Time-weighted average change in \log_{10} viral load from Day 1/Baseline through Day 7 (DAVG₇) as measured in nasal samples by RT-qPCR among subjects in the FAS
- Time-weighted average change in \log_{10} viral load from Day 1/Baseline through Day 7 (DAVG₇) in a subset of FAS subjects whose duration of RSV symptoms prior to the first dose of study medication is \leq median

The time-weighted average change in nasal RSV viral load from Day 1 through Day 7 is defined as:

$$\frac{\sum_{i=a}^{b-1} \{0.5 \times (Y_i + Y_{i+1}) \times (t_{i+1} - t_i)\}}{(t_b - t_a)}$$

where Y_i is the change from Day 1 in RSV \log_{10} viral load at the i^{th} Visit, t is the time at the specified timepoint, a is the baseline assessment at Day 1/Baseline and b is the last assessment at or prior to Day 7. The time-weighted average change (DAVG) provides the average viral burden in change from baseline during the time period of interest.

8.1.3. Secondary Endpoint

Secondary endpoints are:

- Time-weighted average change in FLU-PRO score from Day 1/Baseline through Day 7
- Percent change from study baseline in FEV₁% predicted value at Day 28/End of Study

8.1.4. Exploratory Endpoints

PPD [REDACTED]

[REDACTED]

[REDACTED]

[REDACTED]

[REDACTED]

[REDACTED]

[REDACTED]

[REDACTED]

[REDACTED]

[REDACTED]

[REDACTED]

[REDACTED]

[REDACTED]

[REDACTED]

[REDACTED]

[REDACTED]

[REDACTED]

[REDACTED]

[REDACTED]

[REDACTED]

[REDACTED]

[REDACTED]

The exploratory endpoints for the Optional Registry portion are:

- P [REDACTED]
- P [REDACTED]
- D [REDACTED]
- I [REDACTED]
- I [REDACTED]
- I [REDACTED]
- I [REDACTED]
- I [REDACTED]
- I [REDACTED]
- I [REDACTED]
- I [REDACTED]
- I [REDACTED]
- I [REDACTED]
- I [REDACTED]

8.2. Analysis Conventions

8.2.1. Analysis Sets

8.2.1.1. Efficacy

The FAS will include all randomized subjects who take at least 1 full dose of study drug, and have an RSV viral load greater than or equal to the lower limit of quantification (LLOQ) of the RT-qPCR assay in the pre-dose Day 1/Baseline nasal sample, as determined by RT-qPCR at the central lab. The subgroup analysis set includes subjects who are in the FAS whose duration of RSV symptoms prior to first dose of study medication is \leq median. The FAS and the subgroup analysis set will be used as the primary analysis sets for all summaries and analyses of the primary and secondary efficacy endpoints.

8.2.1.2. Safety

The primary analysis set for safety analyses is defined as all subjects who received at least a full dose of IMP.

All data collected during treatment will be included in the safety summaries.

8.2.1.3. Pharmacokinetics

The PK Analysis Set will include all subjects in the safety analysis set who have evaluable on-study PK measurements.

8.3. Data Handling Conventions

Missing data can have an impact upon the interpretation of the trial data. As this study is of short duration, it is anticipated that missing data will be minimal. In general, values for missing data will not be imputed. For laboratory data, a missing Baseline value will be replaced with a screening value, if available; otherwise it will be treated as normal (ie, Grade 0; no toxicity grade) for the summary of graded laboratory abnormalities. A retest value may be used if the first test is invalidated.

Values will not be imputed for missing vital sign and other safety data; however, a missing Baseline value will be replaced with a Screening value, if available.

Details for the handling of missing data due to subject discontinuation or other reasons, including unusable and spurious data, and rules for determining major and minor protocol deviations will be described in the SAP.

All available data for subjects that do not complete the study will be included in the data listings.

Tables that include both individual subject PK data and summary statistics will present all available data, but only subjects in the PK analysis will be included in the summary statistics.

Viral load data will be log transformed prior to analyses.

8.4. Demographic Data and Baseline Characteristics

Demographic and baseline measurements will be listed by subject and summarized by treatment using standard descriptive summaries or categorical summaries, as appropriate.

Demographic summaries will include but not be limited to sex, race/ethnicity and age. Baseline data will include a summary of body weight, height, BMI, and other baseline characteristics.

8.5. Efficacy Analysis

8.5.1. Primary Analysis

The primary endpoint is the time-weighted average change in nasal RSV viral load (\log_{10} copies/mL) from Day 1/Baseline through Day 7. The primary analysis will be performed on subjects included in the FAS and subjects included in the FAS with \leq median duration of symptoms prior to the first dose of study medication. To test these two co-primary null hypotheses of no difference between the presatovir and placebo treatment groups in the time-weighted average change in RSV viral load in the FAS and in the subgroup, parametric analysis of covariance (ANCOVA) models with corresponding baseline RSV viral load as a continuous variable and stratification factors included as covariates will be used. Adjusted means and 95% CIs will be provided. If stratification leads to small cell sizes, a modification to the stratification, which will be described in the SAP, will be implemented.

The co-primary analyses will be controlled at an overall type I error rate at the 2-sided 0.05 level in which the alpha level for the overall FAS population will be 0.04 and the alpha level for the subgroup population (subjects in the FAS with duration of RSV symptoms prior to first dose of study medication \leq median) will be 0.017, as determined by a grid search accounting for the known correlation of the populations.

8.5.2. Secondary Analyses

The FAS analysis set will be used for all summaries and analyses of secondary endpoints. All secondary endpoints will be analyzed using 2-sided tests to compare treatment differences.

The time-weighted average change in FLU-PRO score from Day 1/Baseline through Day 7 will be analyzed using an ANCOVA model with the baseline FLU-PRO score value and stratification factors as covariates. Adjusted means and a 95% CI will be provided.

The percent change in FEV₁% predicted values from Day 1/Baseline through Day 28/End of Study will be analyzed using an ANCOVA model with study baseline FEV₁% predicted value and stratification factors as covariates. The percent change in FEV₁% predicted values will be calculated as the difference of FEV₁% predicted values at study baseline and Day 28/End of Study, divided by study baseline FEV₁% predicted value and multiplied by 100.

In order to account for multiple hypothesis testing across the primary and secondary endpoints, a family alpha spending rule will be used to control the Type 1 error rate of 0.05. The co-primary endpoint analyses will serve as the gatekeeper for the secondary analyses conducted within each population. If the co-primary null hypothesis is rejected, then the following secondary endpoints will be tested sequentially at the specified alpha-level within each population (ie, $\alpha = 0.04$ and/or $\alpha = 0.017$), respectively, based upon the closed testing procedure {[Dmitrienko et al 2003](#)}.

- Time-weighted average change in FLU-PRO score from Day 1/Baseline through Day 7
- Percent change from study baseline in FEV₁% predicted value at Day 28/End of Study

8.5.3. Exploratory Analyses

Main Study portion (Day 1/Baseline through Day 28/End of Study)

PPD

[Redacted]

[Redacted]

[Redacted]

[Redacted]

[Redacted]

[Redacted]

Optional Registry

PPD

[Redacted]

PPD

8.6. Safety Analysis

All safety data will be listed. Data for the pretreatment and treatment-free follow-up periods will be included in data listings only. Data for the treatment period will be summarized by treatment (active or placebo) using the number of subjects (n and percent) with events/abnormalities for categorical data and using descriptive statistics (n, mean, SD, median, and range) for continuous data.

8.7. Extent of Exposure

A subject's extent of exposure to IMP data will be generated from the IMP administration data. Exposure data will be summarized by treatment group.

8.7.1. Adverse Events

Clinical and laboratory adverse events will be coded using the Medical Dictionary for Regulatory Activities (MedDRA). System Organ Class (SOC), High-Level Group Term (HLGT), High-Level Term (HLT), Preferred Term (PT), and Lower-Level Term (LLT) will be attached to the clinical database.

Events will be summarized on the basis of the date of onset for the event. A treatment-emergent adverse event will be defined as any adverse event that begins on or after the date of first dose of IMP up to Day 28, or any AEs leading to premature discontinuation of IMP.

Summaries (number and percentage of subjects) of treatment-emergent adverse events (by SOC, and PT) will be provided by treatment group.

AEs will also be summarized by relationship to treatment (IMP) and severity.

A listing of AEs will be provided for all subjects who experience an SAE. Data listings will also be provided for subjects who discontinued the study due to any AE, as well as for an SAE.

8.7.2. Laboratory Evaluations

Selected laboratory data will be summarized using only observed data. Data and change from Baseline at all scheduled time points will be summarized.

Graded laboratory abnormalities will be defined using the grading scheme in [Appendix 5](#). Grading of laboratory abnormalities for analysis purposes will be performed by GSI.

Incidence of treatment-emergent laboratory abnormalities, defined as values that increase at least 1 toxicity grade from baseline at any time post baseline up to and including Day 28/End of Study will be summarized by treatment group. If baseline data are missing, then any graded abnormality (ie, at least a Grade 1) will be considered treatment emergent.

Laboratory abnormalities that occur before the first dose of IMP or after the subject has been discontinued from treatment for at least 28 days will be included in a data listing.

8.7.3. Other Safety Evaluations

Vital signs and ECG data will be summarized by the observed data and by the change from baseline at each time point. In comparison to pre-treatment (either screening or pre-dose on study Day 1) values, vital signs, and ECG measurements will additionally be summarized using pre-determined clinically relevant thresholds.

8.8. Pharmacokinetic Analysis

Concentrations of presatovir will be determined in plasma using a validated Bioanalytical assay. Individual subject presatovir concentration-time data will be displayed using scheduled sampling times. Descriptive statistics (eg, n, mean, standard deviation, %CV, median, and range) will be calculated for each sampling time. The pharmacokinetic/pharmacodynamic (PK/PD) relationship may be explored as appropriate.

8.9. Sample Size

Sample size calculations are based on results observed from 3 studies:

- 1) A study that evaluated the efficacy of oral and aerosolized ribavirin treatment for preventing progression from upper to lower respiratory tract infection in hematopoietic cell transplant recipients with RSV infections (unpublished data from [name])
- 2) A study conducted by Zamora et al that evaluated the treatment of RSV infection in LT recipients
- 3) GS-US-218-1227, an on-going Phase 2 study that is evaluating the antiviral effects of presatovir in hospitalized adults with RSV infection.

The sample size calculation assumes the time-weighted average change in RSV log₁₀ viral load from Day 1/Baseline through Day 7 in the placebo group will be -1.5 log₁₀ copies/mL with a corresponding SD of 1.2. Based on these assumptions and the 2:1 allocation ratio to receive presatovir or placebo, with 34 subjects in the presatovir group and 17 subjects in the placebo group, there is at least 85% power to detect a 1.2 log difference in time-weighted average change in log₁₀ viral load between presatovir and placebo using a 2-sided 0.04-level test in the co-primary endpoint including all subjects in the FAS. There is 85% power to detect a 1.5 log difference with 17 subjects in the presatovir group and 9 subjects in the placebo group in the co-primary endpoint analysis of the subjects in the FAS with ≤ median duration of symptoms prior to first dose of study medication using a 2-sided 0.017-level test, assuming a SD of 1.2. Given an evaluable rate of 85%, a total of 60 subjects will need to be randomized into the study.

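### The stated 85% power for the co-primary test in subjects with symptom duration at or below the median does not follow from the plan's own inputs, which give about 68% (74% by normal approximation)

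*Protocol*

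**What the plan says.** Protocol 8.9 gives a power statement for each co-primary test. For the FAS, with 34 presatovir and 17 placebo subjects, a 2-sided 0.04 level and SD 1.2, it says "there is at least 85% power to detect a 1.2 log difference". For the subset with symptom duration at or below the median it says "There is 85% power to detect a 1.5 log difference with 17 subjects in the presatovir group and 9 subjects in the placebo" group, "using a 2-sided 0.017-level test, assuming a SD of 1.2".

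The Protocol synopsis and SAP 1.3 repeat both statements with the same figures. The subgroup level is not a slip in the power text alone. Protocol 8.5.1 says that it "will be 0.017, as determined by a grid search accounting for the known correlation of the populations", and SAP 3.5 and SAP Appendix 2 (boundary 2.379) agree. The planned analysis is an ANCOVA on baseline viral load and the stratification factors (Protocol 8.5.1, SAP 6.1.2). Neither document gives a residual SD or a share of variance explained by these covariates.

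**The concern.** Everything needed to check the subgroup figure is in its own sentence: group sizes, difference, SD, level and sidedness. The neighbouring FAS figure uses twice as many subjects and a less strict level, although for a smaller difference, so the two claims can be tested with one formula.

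The subgroup comparison is a primary hypothesis with its own share of alpha, and it is the gatekeeper for secondary testing in that population (Protocol 8.5.2). If its power is overstated, the chance of missing a true 1.5 log effect is understated, and a reader relying on the 85% could give too much weight to a null result in early presenters.

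**Working it through.** **Inputs** (Protocol 8.9; same figures in the synopsis and SAP 1.3)

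- Subgroup: n1 = 17, n2 = 9, difference 1.5, SD 1.2, 2-sided alpha 0.017
- FAS: n1 = 34, n2 = 17, difference 1.2, SD 1.2, 2-sided alpha 0.04

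**Formula.** Two-sample comparison of means with common SD. The noncentrality is ncp = (difference / SD) / sqrt(1/n1 + 1/n2). Power by t is the noncentral-t probability beyond the critical value on n1 + n2 − 2 df. Power by normal approximation is Φ(ncp − z), where z is the two-sided critical value.

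**Step 1: check the method on the FAS statement.** ncp = (1.2/1.2) / sqrt(1/34 + 1/17) = 3.367. Power is 89.2% by t and 90.5% by normal approximation, so the claim of at least 85% is true. The total also holds: 51/0.85 = 60.

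**Step 2: try to reproduce the subgroup figure.** sqrt(1/17 + 1/9) = 0.412, so ncp = 1.25 / 0.412 = 3.032.

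- t-test, 24 df: critical value 2.565, power **67.9%** (68.0% in 200,000 simulated trials)
- Normal approximation: Φ(3.032 − 2.387) = **74.1%**
- t with the ANCOVA error df of 21 and no variance reduction: 66.9%

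The stated 85% is not reproduced.

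**Step 3: nearby readings of the inputs.**

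| Variant (difference 1.5, SD 1.2) | t | Normal |
|---|---|---|
| 18 vs 9, 2-sided 0.017 | 69.1% | 75.0% |
| 13 vs 13, 2-sided 0.017 | 72.9% | 78.8% |
| 20 vs 10 (half of all 60 randomized), 2-sided 0.017 | 75.0% | 80.0% |
| 17 vs 9, one-sided 0.017 | 77.9% | 81.9% |
| 17 vs 9, 2-sided 0.05 | 82.9% | 85.8% |

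Keeping 17 vs 9 and 2-sided 0.017 but lowering the SD to 1.0 gives 84.9% by t. So at 17 vs 9, two different single changes bring the result to about 85%: alpha 0.05 by normal approximation, or SD 1.0 by t. The plan states neither for this test.

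**Step 4: what 85% power requires, changing one input at a time.**

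- Difference: 1.80 log by t, 1.69 by normal approximation
- SD: 1.00 by t, 1.06 by normal approximation
- Sample size at 2:1: 24 vs 12 gives 84.1% and 26 vs 13 gives 87.5% (both by t)

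**Step 5: what covariate adjustment would have to supply.** Reducing the SD from 1.2 to 1.00 needs R² = 1 − (0.999/1.2)² = 0.31, a multiple correlation of about 0.55 between covariates and outcome.

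**Step 6: the alpha split.** With boundaries 2.054 and 2.379 and correlation sqrt(0.5), the overall two-sided type I error is 0.04996. The split does what SAP Appendix 2 says.

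**The case against.** The strongest objection is that 68% is the power of an unadjusted t-test, while the plan uses ANCOVA. That is correct. With 21 error df, an R² of 0.10, 0.20 or 0.30 would give power of about 72%, 78% or 84%, so the power of the planned test is unknown and could well exceed 68%. But the sentence rests its 85% on an SD of 1.2 and mentions no adjustment, and even R² = 0.30 falls slightly short. The objection is a reason to state the assumption beside the corrected figure; it does not rescue the 85%.

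It can also be said that little depends on this. The FAS test has about 89% power, each hypothesis carries its own alpha, no estimate or error rate changes, and the planned 95% confidence intervals will show the imprecision. All of that stands, and it limits the consequence to a misstated planning figure.

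Three stronger readings are tempting but unsupported:

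- A reader might infer that the sponsor computed power at 0.05 instead of 0.017, especially as SAP 6.1.2 mentions a 2-sided 0.05 level before pointing to Section 3.5. SD 1.0 at 0.017 fits at least as well, and the documents do not settle it.
- A reader might take 32% (100 − 68) as the false-negative risk of the planned analysis. It is the risk for the unadjusted test at a true difference of 1.5 log.
- A reader might infer that the 0.017 boundary should be recomputed because tied durations could push the subgroup above half of the FAS. That depends on a distribution of durations that the documents do not give. It would also conflict with the level fixed throughout both documents, and Appendix 2 shows no error that it would correct.

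**Conclusion.** The subgroup power statement is wrong as written. On the plan's own inputs, power is about 68% by t or 74% by normal approximation, against 85% stated, and the difference detectable with 85% power is about 1.8 log (1.69 by normal approximation). These figures assume normal outcomes with common SD 1.2, exactly 17 and 9 subjects, and no variance explained by covariates. Which input went wrong cannot be determined from the documents. The finding is confined to this one statement: the FAS power, the total of 60 and the alpha split are consistent with the plan's figures.

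**What to change.** In the Protocol synopsis, Protocol 8.9 and SAP 1.3, replace the subgroup sentence with: *about 68% power to detect a 1.5 log difference, or 85% power to detect a 1.8 log difference, with 17 vs 9 subjects at the 2-sided 0.017 level, assuming a SD of 1.2 and no variance reduction from covariates.*

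If the sponsor did rely on a smaller SD or a covariate-adjusted variance, the alternative is to state that value and its source and recompute from it.

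Sample size, alpha levels, analysis model and conduct stay as they are. The cost is a wording change, with a less favourable figure on record. The two protocol edits would need the IRB/IEC submission and approval that Protocol 9.2.1 requires for modifications; the SAP edit would be entered in its revision table.
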